4 PREOPERATIVE/OPERATIVE PARAMETERS

Preoperative and operative parameters for first and second eyes will be reported for each IOL model. The frequency and proportion of eyes with selected responses will be tabulated for categorical data with descriptive statistics used for continuous data.

Statistical comparisons between IOL groups will be performed as described above for demographic data. Two-sided testing with an alpha level of 0.05 will be used for all preoperative and operative parameters.

5 POSTOPERATIVE ANALYSES – PRIMARY AND SECONDARY EFFECTIVENESS ENDPOINTS

5.1 PRIMARY EFFECTIVENESS ENDPOINT

MONOCULAR DISTANCE-CORRECTED NEAR VISUAL ACUITY (DCNVA)

The primary effectiveness endpoint is mean (LogMAR) first-eye, monocular, distance-corrected near visual acuity (40 cm) under photopic conditions at 6 months postoperative. The mean, SD, median, minimum, maximum and two-sided 95% C.I. will be presented by IOL group.

5.2 SECONDARY EFFECTIVENESS ENDPOINTS

5.2.1 MONOCULAR DISTANCE CORRECTED INTERMEDIATE VISUAL ACUITY (DCIVA)

The first secondary endpoint is mean (LogMAR) first-eye, monocular, distance-corrected intermediate visual acuity (66 cm) under photopic conditions at 6 months postoperative. The mean, SD, median, minimum, maximum and two-sided 95% C.I. will be presented by IOL group.

5.2.2 MONOCULAR DISTANCE CORRECTED NEAR VISUAL ACUITY (DCNVA) AT 33 CM

The second secondary endpoint is mean (LogMAR) first-eye, monocular, distance-corrected near visual acuity (33 cm) under photopic conditions at 6 months postoperative. The mean, SD, median, minimum, maximum and two-sided 95% C.I. will be presented by IOL group.

where

5.2.3 MONOCULAR BEST CORRECTED DISTANCE VISUAL ACUITY (BCDVA)

The third secondary effectiveness endpoint is mean (LogMAR) first-eye, monocular, best- corrected distance visual acuity (4 m) under photopic conditions at 6 months postoperative. Results will be compared between lens groups for first eyes using a non-inferiority approach. The mean, SD, median, minimum, maximum and two-sided 95% C.I. will be presented by IOL group.

5.2.4 MONOCULAR DISTANCE-CORRECTED DEFOCUS CURVE

The fourth secondary effectiveness endpoint is monocular distance-corrected defocus curve at 6 months postoperative. The mean of each diopter will be plotted for the range of testing conducted (including positive and negative diopters).

5.2.5 SPECTACLE WEAR

The fifth secondary effectiveness endpoint is decreased spectacle wear determined via the PRO instrument PRSIQ and is defined as wearing glasses or contacts “none of the time” in all 4 conditions (distance vision, intermediate vision, near vision and overall vision) at 6 months postoperative.

5.3 SAFETY ENDPOINTS

PRIMARY SAFETY ENDPOINTS: RATE OF ADVERSE EVENTS

- i. The rate of secondary surgical interventions (SSIs) related to optical properties of the lens in first-eyes of subjects in the investigational lens group

- ii. All SPE types of adverse events reported among first eyes of subjects in the test group will be compared to ISO SPE rates (ISO 11979-7: 2018)

Where

i = indicator for the i^{th} AE

p_i = proportion of Model ZFR00V eyes with the i^{th} AE

θ_i = ISO SPE rates for the i^{th} AE (constant)

Reject the null hypothesis if one-sided p-value ≤ 0.025 .

Success criterion is that the AE rate for the test lens is not statistically significantly higher than the ISO SPE rate ($p > 0.025$).

- iii. All other types (non-SPE) of adverse events

Co-PRIMARY SAFETY ENDPOINTS: MONOCULAR BCDVA 20/40 OR BETTER

- i. For the co-primary safety endpoint of ZFR00V eyes achieving monocular BCDVA of 20/40 or better, the proportion for ZFR00V eyes will be compared to the ISO SPE rate for posterior chamber IOLs (all first eyes)

SECONDARY SAFETY ENDPOINTS: CONTRAST SENSITIVITY

- i. Binocular and monocular first eye contrast sensitivity will be reported by IOL group using descriptive statistics and a two-sided 90% confidence interval for all levels of contrast and lighting conditions. In addition, monocular results will be stratified by pupil size.

For primary and co-primary safety endpoints, additional secondary analyses consisting of second eyes and all eyes (pooling first and second eyes) will also be included.

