4. Monocular distance-corrected defocus curve
5. Spectacle wear

SAFETY

Primary Safety:

1. The rate of secondary surgical interventions (SSIs) related to optical properties of the lens in first eyes of subjects in the test group
2. All SPE types of adverse events, including total SSIs, reported among first eyes of subjects in the test group will be compared to ISO SPE rates.
3. All other types of adverse events (non-SPE) will be analyzed

Co-Primary Safety:

1. The proportion of first eyes in the test group that achieves monocular BCDVA percent of 20/40 or better will be compared to the ISO SPE rate.

Secondary Safety:

The binocular and monocular (first eyes) best-corrected distance contrast sensitivity for the test group will be compared to that of the control (mesopic with and without glare at 1.5, 3, 6, and 12 cpd, photopic with glare at 3, 6, 12, and 18 cpd).

For primary and co-primary safety endpoints, additional secondary analyses consisting of second eyes and all eyes (pooling first and second eyes) will also be included.

OTHER ENDPOINTS

Other endpoints in the study include:

- Binocular distance-corrected defocus
- Monocular (first eye) and binocular mesopic DCNVA at 40 cm
- Monocular (first eye) UCDVA
- Binocular UCDVA, UCIVA, and UCNVA
- Binocular BCDVA and DCNVA at 40 cm
- Medical findings/complications
- Lens findings/complications
- Residual refractive error
- Visual symptoms reported via PRO instrument (Patient Reported Visual Symptoms Questionnaire [PRVSQ])
- Ocular/visual symptoms (non-directed responses to the open-ended question “Are you having any difficulties with your eyes or vision?”)

- Satisfaction and other questionnaire responses

DATA ANALYSIS:

The investigational IOL Model ZFR00V will be compared to the control IOL Model ZCB00. The 6-month postoperative visit is the key analysis time point for all endpoints, although data will be reviewed at other time points as well.

For the primary effectiveness endpoint (DCNVA at 40 cm) and monocular secondary effectiveness endpoints (DCIVA, DCNVA at 33 cm, and BCDVA), the primary analysis population will be a modified Intent-to-Treat (mITT) analysis for all first eyes randomized and implanted with either a test or control lens.

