6.3 SAFETY ENDPOINTS

Primary Safety:

1. The rate of SSIs related to optical properties of the lens in first eyes of subjects in the test group will be analyzed using descriptive statistics and compared to that of the control group.
2. All SPE adverse events, including total SSI, reported among first eyes of subjects in the test group will be compared to ISO SPE rates.
3. All other non-SPE AEs will be analyzed using descriptive statistics comparing the two lens groups.

Co-Primary Safety:

1. The rate of monocular BCDVA 20/40 or better among first eyes of subjects in the test group will be compared to ISO SPE rates.

Additionally, secondary analyses consisting of second eyes and all investigational eyes (pooling first and second eyes together) will also be included for the above primary and co-primary safety endpoints.

Secondary Safety:

As a secondary safety endpoint, the binocular and monocular (first eyes) best-corrected distance contrast sensitivity for the test group will be compared to control (mesopic with and without glare at 1.5, 3, 6, and 12 cpd, photopic with glare at 3, 6, 12, and 18 cpd).

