17. RISK ANALYSIS

POTENTIAL RISKS AND RISK MANAGEMENT

Investigational IOL Model ZFR00V

The investigational IOL Model ZFR00V is designed to provide far vision and a range of intermediate to near vision; however, glasses may still be needed to improve distance vision and/or to have better vision for certain intermediate or near tasks. Some visual symptoms, particularly dysphotopsias such as halos, glare, starbursts, etc., may be expected. Dysphotopsias may become less noticeable over time; however, the IOL may be removed if necessary. There may be a reduction in contrast sensitivity under certain conditions compared to a monofocal lens although contrast sensitivity is expected to be similar to that of TECNIS Multifocal IOLs. Due to the diffractive optic design, the ability to perform some eye treatments (e.g., retinal photocoagulation) may be affected, and caution should be used when interpreting results of autorefractors or wavefront aberrometers that utilize infrared light, or when performing a duochrome test. These risks are not unlike those for other diffractive technology IOLs, but the use of these instruments is not recommended for use in this study.

General Risks of Cataract Surgery and IOL Implantation

There are risks and complications associated with cataract surgery and IOL implantation in general. These can include worsening of vision, hemorrhage, loss of corneal clarity, inflammation, infections, retinal detachment, pupil changes, glaucoma, etc. Complications can result in poor vision, loss of vision or loss of the eye.

Risk Management

Subjects will be closely monitored throughout the trial duration. The occurrence of adverse events and complaints will be assessed at each study visit and reported to the Sponsor according to **Section 11.0**, Adverse Events and Product Complaints.

Additionally, the Sponsor will monitor incoming data following the procedures outlined in **Section 15.0**, Monitoring. The Medical Monitor will ensure subjects are not exposed to additional risks by monitoring serious adverse events, device-related adverse events, and device-deficiencies that could have led to serious adverse events (**Section 15.3**, Safety Monitoring).

POTENTIAL BENEFITS

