6.5 OTHER MONOCULAR CONTRAST SENSITIVITY

In addition to the mean contrast sensitivity analysis in Section 5.3, monocular contrast sensitivity will also be stratified by pupil group. The pupil size corresponding to the contrast testing lighting condition will be used (i.e., mesopic no glare CS will be stratified using mesopic no glare pupil size group). The pupil group for mesopic lighting condition is as follows: ≤ 4.0 mm, > 4.0 to ≤ 5.0 mm and > 5.0 mm; the pupil group for photopic condition is as follows: ≤ 2.5 mm, > 2.5 to < 4.0 mm and ≥ 4.0 mm.

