7 SAMPLE SIZE CALCULATIONS

Study sample sizes are based on the requirements for a Level B modification of a parent lens as well as the requirement for contrast sensitivity testing. The minimum requirements are 100 evaluable test subjects per lens group for Level B and 122 evaluable test subjects per lens group for contrast sensitivity. The screen failure rate is assumed to be 10%, and the dropout rate is assumed to be 10%. To achieve the minimum of 122 evaluable subjects in each IOL group at 6 months postoperative and allowing for screen failures and drop out, up to 150 subjects will be enrolled in each lens group to achieve approximately 135 bilaterally implanted subjects in each lens group.

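### SAP 5.3 visibly specifies only per-lens 90% intervals for contrast sensitivity, although the protocol calls for a comparison with control; the between-lens difference and its interval should be stated.

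*SAP*

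**What the plan says.** Protocol 6.3, under Secondary Safety, states that binocular and first-eye "best-corrected distance contrast sensitivity for the test group will be compared to control". The conditions are "mesopic with and without glare at 1.5, 3, 6, and 12 cpd, photopic with glare at 3, 6, 12, and 18 cpd". The Protocol synopsis says the same: "best-corrected distance contrast sensitivity for the test group will be compared to that of the control".

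SAP 7 rests the sample size on the Level B requirement "as well as the requirement for contrast sensitivity testing". It gives 100 per group for Level B and "122 evaluable test subjects per lens group for contrast sensitivity", so the contrast requirement is the binding one. SAP 7.7 adds only that the ISO 11979-7:2018 criterion is met with 122 per group. It gives no SD, difference, margin, alpha or power for this endpoint.

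Protocol 17 foresees a possible loss: "There may be a reduction in contrast sensitivity under certain conditions compared to a monofocal lens".

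For the analysis, SAP 5.3 says contrast sensitivity "will be reported by IOL group using descriptive statistics and a two-sided 90% confidence interval for all levels of contrast and lighting conditions", with monocular results also stratified by pupil size. SAP 6.5 refers back to this: "In addition to the mean contrast sensitivity analysis in Section 5.3, monocular contrast sensitivity will also be stratified by pupil group". No visible passage gives a between-lens difference, an interval for it, a test, a margin or a success criterion for contrast sensitivity.

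**The concern.** A reader of Protocol 6.3 expects an estimate of how much contrast sensitivity the test lens loses against the monofocal control, with its uncertainty. The visible SAP sentence gives an interval for each lens mean. Two such intervals side by side do not state the uncertainty of their difference, and the natural way to read them, by whether they overlap, is more demanding than a direct comparison at the same confidence level. In a safety comparison that leans towards seeing no difference.

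Elsewhere the SAP states a between-lens comparison when it wants one: for demographics (SAP 3.2), for preoperative and operative parameters (SAP 4), and for BCDVA, where a non-inferiority approach is named (SAP 5.2.3). The contrast item has no such sentence. At stake is whether a modest loss, of the kind Protocol 17 anticipates, is reported in a form from which its size and precision can be read directly.

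**Working it through.** **The plan's own figure.** The 122 cannot be derived, because the documents take it from the ISO criterion and give no inputs. The enrolment chain does reproduce: 150 × 0.9 = 135 implanted, and 135 × 0.9 = 121.5, about 122 evaluable per group.

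**Inputs.** n = 122 per lens (SAP 7). Two-sided 90% level (SAP 5.3). Default alpha 0.05 two-sided, 0.025 one-sided (SAP 2.3). Assumptions: equal SDs in the two groups and a normal approximation. The contrast SD is not given, so results are in SD units first, then in log units for assumed SDs of 0.2, 0.3 and 0.4.

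**Thresholds in SD units.**
- Half-width of one lens's 90% interval: 1.645/√122 = 0.149 SD.
- Two such intervals separate when the observed means differ by more than 2 × 0.149 = 0.298 SD.
- Standard error of the difference: √(2/122) = 0.128 SD.
- A 90% interval for the difference excludes zero beyond 1.645 × 0.128 = 0.211 SD.
- A 95% interval for the difference excludes zero beyond 1.960 × 0.128 = 0.251 SD.
- Separation of the two 90% intervals therefore corresponds to z = 0.298/0.128 = 2.33, a two-sided level of 0.02.

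**In log units (assumed SD).**

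| SD | 90% interval for the difference | 95% interval for the difference | Per-lens 90% intervals separate |
|---|---|---|---|
| 0.2 | 0.042 | 0.050 | 0.060 |
| 0.3 | 0.063 | 0.075 | 0.089 |
| 0.4 | 0.084 | 0.100 | 0.119 |

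At SD 0.3 the gap is 0.089 − 0.063 = 0.026 log units against a 90% interval, and 0.089 − 0.075 = 0.014 against the 95% interval that matches the SAP default.

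**How often it matters.** For a true loss of d SD, the chance that the per-lens intervals separate is Φ((d − 0.298)/0.128). The chance that the difference interval excludes zero on the loss side is Φ(d/0.128 − 1.645) at 90%, or with 1.960 at 95%.

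| True loss | Per-lens intervals separate | 90% difference interval excludes zero | 95% difference interval excludes zero |
|---|---|---|---|
| 0.30 SD | 51% | 76% | 65% |
| 0.40 SD | 79% | 93% | 88% |
| 0.50 SD | 94% | 99% | 97% |

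**Is 122 enough for a difference interval?** The loss detectable with 90% power is (1.645 + 1.282) × 0.128 = 0.37 SD at one-sided 0.05, or (1.960 + 1.282) × 0.128 = 0.42 SD at one-sided 0.025. A between-lens interval needs no more subjects.

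**Number of intervals.** 3 lighting conditions × 4 frequencies × 2 (monocular, binocular) = 24. If the lenses did not differ, 24 × 0.10 = 2.4 of the 90% intervals, or 24 × 0.05 = 1.2 of the 95% intervals, would be expected to exclude zero by chance.

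**The case against.** Four points can be made on the other side.

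1. *The public text is incomplete.* The contents list names Protocol 20.2 and 20.3, which are not shown. SAP 2.5 is empty, the SAP's list of analysis tables is absent, and other items in SAP 5.3 have visible gaps. SAP 5.2.3 plans a comparison although its only visible interval is also per lens. A reader might infer that the SAP contains no between-lens analysis of contrast sensitivity. The documents do not support that, and the point holds for the visible text only. Still, the contrast item reads as complete sentences, and SAP 6.5 refers back to it simply as an analysis of means.

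2. *Comparison may mean descriptive comparison.* Protocol 6.3 uses the word that way for secondary surgical interventions and for the other adverse events. Nor does the 122 come from a stated power calculation for a difference. A reader might infer that the trial cannot answer the question for which it was sized. That does not follow. What stands is narrower: even a descriptive comparison is better served by the difference and its interval.

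3. *No overlap rule is written.* This is correct. The thresholds above show what would happen under such a reading; they do not describe a planned criterion. SAP 2.3 says descriptive statistics typically include N, mean and SD, so a reader can rebuild the difference interval. The stronger claim that a loss would be hidden is not supported.

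4. *The 90% benchmark flatters the concern.* Against the SAP's default level the gap roughly halves, as the working shows. The documents also give no clinical threshold for contrast loss against which to weigh it.

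The 90% level, where 95% is used for the visual acuity endpoints, may itself mean that an interval for the difference was intended. If so, the sentence does not say it.

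**Conclusion.** The concern holds in a limited form. On the visible text, the analysis of the named secondary safety endpoint stops at per-lens intervals, and these do not estimate the comparison stated in Protocol 6.3. The practical effect is modest. Observed losses between about 0.21 and 0.30 SD (0.25 to 0.30 SD against a 95% interval) would leave the lens intervals overlapping although the difference interval excludes zero. True losses of 0.5 SD or more would separate even the per-lens intervals in about 94% of trials.

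This rests on equal SDs, 122 evaluable subjects per group, and a reader who goes by overlap. The log-unit figures rest also on assumed SDs. It is a worthwhile clarification of a safety analysis. It does not show that the sample size is wrong or that the trial is unable to detect a contrast loss.

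**What to change.** In SAP 5.3, add that the test-minus-control difference in mean log contrast sensitivity will be reported with its two-sided confidence interval for each spatial frequency and lighting condition, monocularly (first eyes) and binocularly. Keep the per-lens descriptive statistics. Either give the reason for the 90% level or use 95%, in line with SAP 2.3. State that the comparison is estimation without a success margin, unless one is prespecified, and that the 24 intervals are unadjusted and to be read as descriptive. If the 90% interval was already meant for the difference, reword the sentence to say so.

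The cost is one amended SAP passage and one column in the planned tables. No new data, visits or subjects are needed.

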6 POSTOPERATIVE ANALYSIS: OTHER ENDPOINTS

6.1 OTHER INTERMEDIATE AND NEAR VISUAL ACUITY ENDPOINTS

Other intermediate and near endpoints include binocular UCIVA, binocular UCNVA at 40 cm, binocular DCNVA at 40 cm and monocular and binocular mesopic DCNVA at 40 cm. These endpoints will be evaluated at 6 months using the safety population.

In addition, the frequency and proportion of first eyes and binocular subjects achieving each line of visual acuity will be reported at 6 months.

6.2 OTHER DEFOCUS CURVE ENDPOINTS

Binocular defocus data for the test group will be analyzed with the same method as that used for the monocular defocus curve described in the secondary effectiveness endpoint. In addition, monocular results will also be stratified by pupil group (≤ 2.5 mm, > 2.5 mm to < 4.0 mm and ≥ 4.0 mm) using pupil size under photopic no glare condition.

6.3 OTHER DISTANCE VISUAL ACUITY

In addition to the mean BCDVA analysis in 5.2.3, the proportion of first eyes achieving each acuity line equivalent for monocular BCDVA will also be reported over time. Descriptive statistics with two-sided 95% CI for mean LogMAR and frequency achieving acuity by line will also be reported for binocular BCDVA, monocular UCDVA and binocular UCDVA. To evaluate the effect of residual refractive error on monocular UCDVA, a scatterplot of residual refractive error vs. UCDVA will be presented by IOL group.

6.4 MEDICAL/LENS FINDINGS

Rates of postoperative medical and lens findings will be tabulated with the frequency and proportion of eyes with these events reported over time by IOL group. As mentioned above in Section 5.3.1 Safety Endpoints: Rates of Adverse Events, medical complication rates listed in ISO-11979 will be compared to the ISO SPE rates for ZFR00V first eyes

Reporting of cumulative complications and cumulative adverse events (occurring at any time postoperative either at standard visits or interim visits) will include data from all study eyes implanted.

6.5 OTHER MONOCULAR CONTRAST SENSITIVITY

In addition to the mean contrast sensitivity analysis in Section 5.3, monocular contrast sensitivity will also be stratified by pupil group. The pupil size corresponding to the contrast testing lighting condition will be used (i.e., mesopic no glare CS will be stratified using mesopic no glare pupil size group). The pupil group for mesopic lighting condition is as follows: ≤ 4.0 mm, > 4.0 to ≤ 5.0 mm and > 5.0 mm; the pupil group for photopic condition is as follows: ≤ 2.5 mm, > 2.5 to < 4.0 mm and ≥ 4.0 mm.

6.6 MANIFEST REFRACTION

Descriptive analysis and two-sided 95% confidence interval of refractive sphere, cylinder, spherical equivalent (SEQ) and postoperatively measured SEQ minus intended SEQ will be reported by IOL groups for both eyes. Since refraction was performed at 4M, 0.25D will be subtracted from the sphere value. Refractive data will then be converted to plus cylinder notation (see Appendix II).

MRSE is then calculated by the following formula: MRSE = sphere + ½ cylinder.

In addition, the frequency and proportion of each eye within certain diopter categories (≤ 0.50 , $0.51-1.00$, $1.01-1.50$, $1.51-2.00$, >2.00) will be tabulated for refractive cylinder and postoperatively measured SEQ minus intended SEQ by IOL groups for both eyes.

6.7 IOL POWER CONSTANT ANALYSIS

Descriptive statistics will be provided for IOL power constant analyses with refractive data at 6 months used for the evaluation.

6.8 FUNDUS VISUALIZATION

The fundus exam findings (within normal limits vs. abnormal) and ability to adequately visualize the fundus (adequate vs. not adequate) will be reported by IOL groups. The frequency and proportion with each outcome will be tabulated by IOL groups.

6.9 NON-DIRECTED OCULAR/VISUAL SYMPTOMS

Rates of postoperative non-directed ocular/visual symptoms will be tabulated with the frequency and proportion of eyes with these events reported over time by IOL group.

6.10 VISUAL SYMPTOMS VIA PRO INSTRUMENT

Visual symptom data obtained from the PRVSQ instrument at 6-month will be reported for subjects who have received the same test lenses or same control lenses in both eyes. The frequency and proportion of subjects with a given response will be reported by IOL group.

